Appendix B Adverse event definitions and additional safety information

B 1 Definition of adverse events

An adverse event is the development of any untoward medical occurrence in a subject or clinical study subject administered a medicinal product and which does not necessarily have a causal relationship with this treatment. An AE can therefore be any unfavourable and unintended sign (e.g. an abnormal laboratory finding), symptom (for example nausea, chest pain), or disease temporally associated with the use of a medicinal product, whether or not considered related to the medicinal product.

The term AE is used to include both serious and non-serious AEs and can include a deterioration of a pre-existing medical occurrence. An AE may occur at any time, including run-in or washout periods, even if no Study treatment has been administered.

B 2 Definitions of serious adverse event

A serious adverse event is an AE occurring during any study phase (i.e., run-in, treatment, washout, follow-up), that fulfils one or more of the following criteria:

- Results in death
- Is immediately life-threatening
- Requires in-subject hospitalisation or prolongation of existing hospitalisation
- Results in persistent or significant disability or incapacity
- Is a congenital abnormality or birth defect
- Is an important medical event that may jeopardise the subject or may require medical treatment to prevent one of the outcomes listed above.

B 3 Life threatening

‘Life-threatening’ means that the subject was at immediate risk of death from the AE as it occurred or it is suspected that use or continued use of the product would result in the subject’s death. ‘Life-threatening’ does not mean that had an AE occurred in a more severe form it might have caused death (e.g., hepatitis that resolved without hepatic failure).

B 4 Hospitalisation

Outpatient treatment in an emergency room is not in itself a serious AE, although the reasons for it may be (e.g., bronchospasm, laryngeal oedema). Hospital admissions and/or surgical operations planned before or during a study are not considered AEs if the illness or disease existed before the subject was enrolled in the study, provided that it did not deteriorate in an unexpected way during the study.

B 5 Important medical event or medical treatment

Medical and scientific judgement should be exercised in deciding whether a case is serious in situations where important medical events may not be immediately life threatening or result in death, hospitalisation, disability or incapacity but may jeopardize the subject or may require medical treatment to prevent one or more outcomes listed in the definition of serious. These should usually be considered as serious.

Simply stopping the suspect drug does not mean that it is an important medical event; medical judgement must be used.

- Angioedema not severe enough to require intubation but requiring iv hydrocortisone treatment
- Hepatotoxicity caused by paracetamol (acetaminophen) overdose requiring treatment with N-acetylcysteine
- Intensive treatment in an emergency room or at home for allergic bronchospasm
- Blood dyscrasias (e.g. neutropenia or anaemia requiring blood transfusion, etc.) or convulsions that do not result in hospitalisation
- Development of drug dependency or drug abuse

B 6 Intensity rating scale:

1. mild (awareness of sign or symptom, but easily tolerated)
2. moderate (discomfort sufficient to cause interference with normal activities)
3. severe (incapacitating, with inability to perform normal activities)

It is important to distinguish between serious and severe AEs. Severity is a measure of intensity whereas seriousness is defined by the criteria in Appendix B 2. An AE of severe intensity need not necessarily be considered serious. For example, nausea that persists for several hours may be considered severe nausea, but not a SAE unless it meets the criteria shown in Appendix B 2. On the other hand, a stroke that results in only a limited degree of disability may be considered a mild stroke but would be a SAE when it satisfies the criteria shown in Appendix B 2.

B 7 A Guide to Interpreting the Causality Question

When assessing causality consider the following factors when deciding if there is a ‘reasonable possibility’ that an AE may have been caused by the drug.

- Time Course. Exposure to suspect drug. Has the subject actually received the suspect drug? Did the AE occur in a reasonable temporal relationship to the administration of the suspect drug?
- Consistency with known drug profile. Was the AE consistent with the previous knowledge of the suspect drug (pharmacology and toxicology) or drugs of the same

pharmacological class? Or could the AE be anticipated from its pharmacological properties?

- De-challenge experience. Did the AE resolve or improve on stopping or reducing the dose of the suspect drug?
- No alternative cause. The AE cannot be reasonably explained by another aetiology such as the underlying disease, other drugs, other host or environmental factors.
- Re-challenge experience. Did the AE reoccur if the suspected drug was reintroduced after having been stopped? AstraZeneca would not normally recommend or support a re-challenge.
- Laboratory tests. A specific laboratory investigation (if performed) has confirmed the relationship.

In difficult cases, other factors could be considered such as:

- Is this a recognized feature of overdose of the drug?
- Is there a known mechanism?

Causality of ‘related’ is made if following a review of the relevant data, there is evidence for a ‘reasonable possibility’ of a causal relationship for the individual case. The expression ‘reasonable possibility’ of a causal relationship is meant to convey, in general, that there are facts (evidence) or arguments to suggest a causal relationship.

The causality assessment is performed based on the available data including enough information to make an informed judgment. With limited or insufficient information in the case, it is likely that the event(s) will be assessed as ‘not related’.

Causal relationship in cases where the disease under study has deteriorated due to lack of effect should be classified as no reasonable possibility.

B 8 Medication Error

For the purposes of this clinical study a medication error is an unintended failure or mistake in the treatment process for an AstraZeneca investigational product that either causes harm to the participant or has the potential to cause harm to the participant.

A medication error is not lack of efficacy of the drug, but rather a human or process related failure while the drug is in control of the study site staff or participant.

Medication error includes situations where an error:

- Occurred
- Was identified and intercepted before the participant received the drug

- Did not occur, but circumstances were recognized that could have led to an error

Examples of events to be reported in clinical studies as medication errors:

- Drug name confusion
- Dispensing error e.g. medication prepared incorrectly, even if it was not actually given to the participant
- Drug not administered as indicated, for example, wrong route or wrong site of administration
- Drug not taken as indicated e.g. tablet dissolved in water when it should be taken as a solid tablet
- Drug not stored as instructed e.g. kept in the fridge when it should be at room temperature
- Wrong participant received the medication (excluding IxRS errors)
- Wrong drug administered to participant (excluding IxRS errors)

Examples of events that **do not** require reporting as medication errors in clinical studies:

- Errors related to or resulting from IxRS - including those which lead to one of the above listed events that would otherwise have been a medication error
- Participant accidentally missed drug dose(s) e.g. forgot to take medication
- Accidental overdose (will be captured as an overdose)
- Participant failed to return unused medication or empty packaging
- Errors related to background and rescue medication, or standard of care medication in open label studies, even if an AZ product

Medication errors are not regarded as AEs but AEs may occur as a consequence of the medication error.

Appendix C Cardiovascular related events

C 1 Myocardial Infarctions (MI)

MIs are not endpoints in this study but unstable angina and myocardial infarction should be recorded as SAEs if serious criteria are met and additional information be collected in specific eCRF. The diagnoses of unstable angina and MI should adhere to the standardised definitions for endpoints (Hicks et al 2018) described in Appendix [C 2](#)

C 2 Diagnosis of MI and Unstable Angina

Myocardial infarction (MI)

The diagnosis of an MI should be made according to standard clinical practice but is expected to align with the criteria from Third Universal Definition of MI, i.e. detection of a rise and/or fall of cardiac biomarkers such as troponin and at least one of the following: typical clinical symptoms, ischaemic ECG findings, imaging evidence of myocardial injury, or detection of an intracoronary thrombus by angiography or autopsy ([Thygesen et al 2012](#)).

The diagnosis should be made by, or in consultation with, a cardiologist. The findings supporting the diagnosis should be documented in the description of the SAE in the eCRF.

Unstable Angina (UA)

Unstable Angina (UA) is not an endpoint in this study but should be recorded as SAEs (and DAEs when appropriate). The diagnosis of an UA should be made according to standard clinical practice but is expected to align with the following definition:

The diagnosis of unstable angina will require ischemic chest pain (or equivalent) at rest ≥ 10 minutes in duration considered to be myocardial ischemia upon final diagnosis and prompting hospitalisation within 24 hours of the most recent symptoms, and without elevation in cardiac biomarkers of necrosis, and the presence of objective evidence of ischemia as defined by at least 1 of the following criteria:

1. New or worsening ST or T wave changes in ≥ 2 anatomically contiguous leads on a resting ECG (in the absence of LVH and LBBB):
 - a) transient (< 20 minutes) ST elevation at the J point ≥ 0.2 mV in men (> 0.25 mV in men < 40 years old) or ≥ 0.15 mV in women in leads V2-V3 and/or ≥ 0.1 mV in other leads, or
 - b) horizontal or down-sloping ST depression ≥ 0.10 mV, or
 - c) T-wave inversion ≥ 0.2 mV
2. Definite evidence of myocardial ischemia on myocardial scintigraphy (clear reversible perfusion defect), stress echocardiography (reversible wall motion abnormality), or MRI (myocardial perfusion deficit under pharmacologic stress) that is believed to be responsible for the myocardial ischemic symptoms/signs.
3. Angiographic evidence of $\geq 70\%$ lesion and/or thrombus in an epicardial coronary artery that is believed to be responsible for the myocardial ischemic symptoms/signs.

C 3 Stroke

Stroke is not an endpoint in this study but should be recorded as SAEs if serious criteria are met, with additional information e.g. classification of stroke type (ischaemic, haemorrhagic, or undetermined) collected in a specific eCRF.

The diagnosis of stroke should be made according to standard clinical practice and align with the definition for stroke in the standardized definitions for endpoints (Hicks et al 2018) described in Appendix C 4 and be differentiated vs Transient Ischaemic Attack (TIA).

C 4 Definition of Stroke and Transient Ischemic Attack

The distinction between an Ischemic Stroke and a Transient Ischemic Attack is the presence of infarction. Persistence of symptoms ≥ 24 hours or until death³ is an acceptable indicator of acute infarction in the absence of imaging evidence of infarction.

Transient Ischemic Attack

Transient ischemic attack (TIA) is defined as a transient episode of focal neurological dysfunction caused by brain, spinal cord, or retinal ischemia, *without* acute infarction.

Stroke

Stroke is defined as an acute episode of focal or global neurological dysfunction caused by brain, spinal cord, or retinal vascular injury as a result of haemorrhage or infarction.

Classification:

A. Ischemic Stroke

Ischemic stroke is defined as an acute episode of focal cerebral, spinal, or retinal dysfunction caused by infarction of central nervous system tissue.

Haemorrhage may be a consequence of ischemic stroke. In this situation, the stroke is an ischemic stroke with haemorrhagic transformation and not a haemorrhagic stroke.

B. Haemorrhagic Stroke

Haemorrhagic stroke is defined as an acute episode of focal or global cerebral or spinal dysfunction caused by non-traumatic intraparenchymal, intraventricular, or subarachnoid haemorrhage. NOTE: Subdural hematomas are intracranial haemorrhagic events and not strokes.

C. Undetermined Stroke

Undetermined stroke is defined as an acute episode of focal or global neurological dysfunction caused by presumed brain, spinal cord, or retinal vascular injury as a result of haemorrhage or infarction but with insufficient information to allow categorization as either ischemic or haemorrhagic.

References:

Hicks KA et al. 2017 Cardiovascular and Stroke Endpoint Definitions for Clinical Trials. J Am Coll Cardiol 2018;71:1021–34 <https://doi.org/10.1016/j.jacc.2017.12.048>

Draft Definitions for CDISC August 20, 2014

Appendix D Genetics

D 1 Use/analysis of DNA

Genetic variation may impact a subject's response to therapy, susceptibility to, and severity and progression of disease. Variable response to therapy may be due to genetic determinants that impact drug absorption, distribution, metabolism, and excretion; mechanism of action of the drug; disease aetiology; and/or molecular subtype of the disease being treated. Therefore, where local regulations and IRB/IEC allow, a blood sample will be collected for DNA analysis from consenting subjects.

AstraZeneca intends to collect and store DNA for genetic research to explore how genetic variations may affect clinical parameters, risk and prognosis of diseases, and the response to medications. Genetic research may lead to better understanding of diseases, better diagnosis of diseases or other improvements in health care and to the discovery of new diagnostics, treatments or medications.

In addition, collection of DNA samples from populations with well described clinical characteristics may lead to improvements in the design and interpretation of clinical trials and, possibly, to genetically guided treatment strategies.

Genetic research may consist of the analysis of the structure of the subject's DNA, i.e. the entire genome.

The results of genetic analyses may be reported in the clinical study report (CSR) or in a separate study summary.

The sponsor will store the DNA samples in a secure storage space with adequate measures to protect confidentiality.

The samples will be retained while research on heart failure with preserved ejection fraction continues but no longer than 15 years or other period as per local requirements.

D 2 Genetic research plan and procedures

Selection of genetic research population

Study selection record

All subjects will be asked to participate in this genetic research. Participation is voluntary and if a subject decline to participate there will be no penalty or loss of benefit. The subject will not be excluded from any aspect of the main study.

Inclusion criteria

- For inclusion in this genetic research, subjects must fulfil all of the inclusion criteria described in the main body of the Clinical Study Protocol **and** Provide informed consent for the genetic sampling and analyses.

Exclusion criteria

Exclusion from this genetic research may be for any of the exclusion criteria specified in the main study or any of the following:

- Previous allogeneic bone marrow transplant
- Non-leukocyte depleted whole blood transfusion in 120 days of genetic sample collection

Withdrawal of consent for genetic research:

Subjects may withdraw from this genetic research at any time, independent of any decision concerning participation in other aspects of the main study. Voluntary withdrawal will not prejudice further treatment. Procedures for withdrawal are outlined in Section 7 of the main Clinical Study Protocol.

Collection of samples for genetic research

The blood sample for genetic research will be obtained from the subjects at Visit 2. Although DNA is stable, early sample collection is preferred to avoid introducing bias through excluding subjects who may withdraw due to an adverse event (AE), such subjects would be important to include in any genetic analysis. If for any reason the sample is not drawn at Visit 2, it may be taken at any visit until the last study visit. Only one sample should be collected per subject for genetics during the study. Samples will be collected, labelled, stored, and shipped as detailed in the Laboratory Manual.

Coding and storage of DNA samples

The processes adopted for the coding and storage of samples for genetic analysis are important to maintain subject confidentiality. Samples will be stored for a maximum of 15 years, from the date of last subject last visit, after which they will be destroyed. DNA is a finite resource that is used up during analyses. Samples will be stored and used until no further analyses are possible or the maximum storage time has been reached.

An additional second code will be assigned to the blood sample either before or at the time of DNA extraction replacing the information on the sample tube. Thereafter, the sample will be identifiable only by the second, unique number. This number is used to identify the sample and corresponding data at the AstraZeneca genetics laboratories, or at the designated organisation. No personal details identifying the individual will be available to any person (AstraZeneca employee or designated organisations working with the DNA).

The link between the subject enrolment/randomisation code and the second number will be maintained and stored in a secure environment, with restricted access at AstraZeneca or designated organisations. The link will be used to identify the relevant DNA samples for analysis, facilitate correlation of genotypic results with clinical data, allow regulatory audit, and permit tracing of samples for destruction in the case of withdrawal of consent.

Ethical and regulatory requirements

The principles for ethical and regulatory requirements for the study, including this genetics research component, are outlined in Appendix A.

Informed consent

The genetic component of this study is optional and the subject may participate in other components of the main study without participating in the genetic component. To participate in the genetic component of the study the subject must sign and date both the consent form for the main study and the genetic component of the study. Copies of both signed and dated consent forms must be given to the subject and the original filed at the study centre. The Principal Investigator(s) is responsible for ensuring that consent is given freely and that the subject understands that they may freely withdrawal from the genetic aspect of the study at any time.

Subject data protection

AstraZeneca will not provide individual genotype results to subjects, any insurance company, any employer, their family members, general physician unless required to do so by law.

Extra precautions are taken to preserve confidentiality and prevent genetic data being linked to the identity of the subject. In exceptional circumstances, however, certain individuals might see both the genetic data and the personal identifiers of a subject. For example, in the case of a medical emergency, an AstraZeneca Physician or an investigator might know a subject's identity and also have access to his or her genetic data. In addition, Regulatory authorities may require access to the relevant files, though the subject's medical information and the genetic files would remain physically separate.

Data management

Any genotype data generated in this study will be stored at a secure system at AstraZeneca and/or designated organizations to analyse the samples.

AstraZeneca and its designated organisations may share summary results (such as genetic differences from groups of individuals with a disease) from this genetic research with other researchers, such as hospitals, academic organisations or health insurance companies. This can be done by placing the results in scientific databases, where they can be combined with the results of similar studies to learn even more about health and disease. The researchers can only use this information for health-related research purposes. Researchers may see summary results but they will not be able to see individual subject data or any personal identifiers.

Some or all of the clinical datasets from the main study may be merged with the genetic data in a suitable secure environment separate from the clinical database.

Statistical methods and determination of sample size

The number of subjects that will agree to participate in the genetic research is unknown. It is therefore not possible to establish whether sufficient data will be collected to allow a formal statistical evaluation or whether only descriptive statistics will be generated. A Statistical Analysis Plan may be prepared where appropriate.

Appendix E Handling of Human Biological Samples

E 1 Chain of custody of biological samples

A full chain of custody is maintained for all samples throughout their lifecycle.

The Investigator at each centre keeps full traceability of collected biological samples from the subjects while in storage at the centre until shipment or disposal (where appropriate).

The sample receiver keeps full traceability of the samples while in storage and during use until used or disposed of or until further shipment and keeps documentation of receipt of arrival.

AstraZeneca will keep oversight of the entire life cycle through internal procedures, monitoring of study sites, auditing or process checks, and contractual requirements of external laboratory providers

Samples retained for further use will be stored in the AZ-assigned biobanks and will be registered by the AstraZeneca Biobank Team during the entire life cycle.

If required, AstraZeneca will ensure that remaining biological samples are returned to the site according to local regulations or at the end of the retention period, whichever is the sooner.

E 2 Withdrawal of Informed Consent for donated biological samples

If a subject withdraws consent to the use of donated biological samples, the samples will be disposed of/destroyed, and the action documented. If samples are already analysed, AstraZeneca is not obliged to destroy the results of this research.

As collection of the biological sample(s) is an integral part of the study, then the subject is withdrawn from further study participation.

The Investigator:

- Ensures subjects' withdrawal of informed consent to the use of donated samples is notified immediately to AstraZeneca
- Ensures that biological samples from that subject, if stored at the study site, are immediately identified, disposed of /destroyed, and the action documented
- Ensures the organization(s) holding the samples is/are informed about the withdrawn consent immediately and that samples are disposed of/destroyed, the action documented and the signed document returned to the study site
- Ensures that the subject and AstraZeneca are informed about the sample disposal.

AstraZeneca ensures the organizations holding the samples is/are informed about the withdrawn consent immediately and that samples are disposed of/destroyed and the action documented and returned to the study site.

E 3 International Airline Transportation Association (IATA) 6.2 Guidance Document

LABELLING AND SHIPMENT OF BIOHAZARD SAMPLES

International Airline Transportation Association (IATA) classifies biohazardous agents into 3 categories (http://www.iata.org/whatwedo/cargo/dangerous_goods/infectious_substances.htm). For transport purposes the classification of infectious substances according to risk groups was removed from the Dangerous Goods Regulations in the 46th edition (2005). Infectious substances are now classified either as Category A, Category B or Exempt. There is no direct relationship between Risk Groups and Categories A and B.

Category A Infectious Substances are infectious substances in a form that, when exposure to it occurs, is capable of causing permanent disability, life-threatening or fatal disease in otherwise healthy humans or animals. Category A pathogens are e.g., Ebola, Lassa fever virus:

- Are to be packed and shipped in accordance with IATA Instruction 602.

Category B Infectious Substances are infectious Substances that do not meet the criteria for inclusion in Category A. Category B pathogens are e.g., Hepatitis A, B, C, D, and E viruses, Human immunodeficiency virus types 1 and 2. They are assigned the following UN number and proper shipping name:

- UN 3373 – Biological Substance, Category B
- Are to be packed in accordance with UN3373 and IATA 650

Exempt - all other materials with minimal risk of containing pathogens

- Clinical trial samples will fall into Category B or exempt under IATA regulations
- Clinical trial samples will routinely be packed and transported at ambient temperature in IATA 650 compliant packaging
(http://www.iata.org/whatwedo/cargo/dangerous_goods/infectious_substances.htm)
- **Biological samples transported in dry ice require additional dangerous goods specification for the dry-ice content**
- IATA compliant courier and packaging materials should be used for packing and transportation and packing should be done by an IATA certified person, as applicable
- Samples routinely transported by road or rail are subject to local regulations which require that they are also packed and transported in a safe and appropriate way to contain any risk of infection or contamination by using approved couriers and packaging/containment materials at all times. The IATA 650 biological sample containment standards are encouraged wherever possible when road or rail transport is used.

Appendix F Actions required in cases of increases in liver biochemistry and evaluation of Hy's Law (not applicable)

Appendix G Medical device incidents: definition and procedures for recording, evaluating, follow-up, and reporting (not applicable)

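### Appendix E 2 does not exempt the optional genetic sample when it ends study participation on withdrawal of sample consent; read literally, it conflicts with Appendix D 2

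*Protocol*

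**What the plan says.** Two appendices deal with a subject who takes back consent for a sample.

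**Appendix E 2** (withdrawal of consent for donated biological samples) opens with the trigger and the handling: "If a subject withdraws consent to the use of donated biological samples, the samples will be disposed of/destroyed, and the action documented". If analyses have already been done, "AstraZeneca is not obliged to destroy the results of this research". It then states the consequence for the subject: "As collection of the biological sample(s) is an integral part of the study, then the subject is withdrawn from further study participation". The investigator's steps follow directly: notify the sponsor, dispose of samples held at the site, inform other holders, and confirm disposal to the subject and the sponsor. No sample type is named or set apart.

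**Appendix D 2** (genetic research) gives a different rule for the genetic sample: "Subjects may withdraw from this genetic research at any time, independent of any decision concerning participation in other aspects of the main study". On subjects who decline, it says: "The subject will not be excluded from any aspect of the main study". Its informed-consent paragraph adds: "The genetic component of this study is optional and the subject may participate in other components of the main study". Section 8.9 and footnote 5 of the Schedule of Activities also call the genetic sample optional.

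On procedure, D 2 says: "Procedures for withdrawal are outlined in Section 7 of the main Clinical Study Protocol". On destruction, it says only that the link between the subject code and the sample code will, among other uses, "permit tracing of samples for destruction in the case of withdrawal of consent".

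**The concern.** E 2 justifies ending participation by saying that sampling is integral to the study. That cannot be true of a sample the protocol repeatedly calls optional. Because E 2 makes no exception, its wording nevertheless covers that sample.

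What is at stake is follow-up of individual patients. The primary analysis (Section 9.4.1.1) follows the intention-to-treat principle and uses adjudicated first events up to the primary analysis censoring date. A patient removed under E 2 would stop contributing heart-failure hospitalisations and urgent visits while still willing to be followed.

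The protocol softens the loss. Section 7.3 lets the sponsor keep data already collected and asks for vital status at study closure, and Section 9.3 keeps every randomised patient in the full analysis set. But vital status from public sources does not recover heart-failure events, and it is a weak basis for separating cardiovascular from other deaths.

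**Working it through.** The protocol states no figure on this point, so the check is a comparison of texts. The test case is a randomised patient who withdraws consent for the genetic sample only and is content to remain in the trial.

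1. **Does the E 2 trigger apply?** It refers to donated biological samples without qualification. The genetic sample is a donated biological sample, so on the wording it does.

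2. **Is the consequence conditional?** No. The sentence begins with *As*, not *If*. It asserts that sampling is integral; it does not confine the rule to samples that are.

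3. **Does the context limit E 2 to mandatory samples?** The mandatory samples are NT-proBNP, creatinine and HbA1c at Visit 1 (Section 8.1.1), with creatinine repeated later. The word *integral* suits them. The surrounding text points the other way:
   - Appendix E 1 extends to samples kept for further use in biobanks.
   - E 2 speaks of research results.
   - The only samples the protocol describes as stored for research are the genetic ones (Table 3, Appendix D 1). Section 8.10 marks biomarkers as not applicable.

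4. **What does D 2 give for the same patient?** Leaving the genetic research is separate from participation in the rest of the study, so the patient stays.

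5. **Does any text say which appendix governs?** None was found. Section 8.9 refers the reader to Appendix D for destruction of these samples. Appendix D offers tracing and a reference to Section 7. Sections 7.1 to 7.3 cover stopping treatment, modified follow-up, loss to follow-up and withdrawal from the study, but not samples. The site's disposal steps appear only in E 2, directly below the participation sentence.

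| Question for the test case | Appendix D 2 | Appendix E 2, literal |
|---|---|---|
| Sample status | Optional | Integral |
| Sample | Traced for destruction | Disposed of and documented |
| Main-study participation | Continues | Ends |

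The two agree on the sample and disagree on participation.

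6. **How many patients?** This cannot be derived. Appendix D 2 says that uptake of the genetic research is unknown, and the protocol gives no rate of sample-consent withdrawal. None of the stated design figures (1117 events, approximately 6100 patients, a final two-sided level of 4.980%) depends on the rule.

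**The case against.** The strongest reply is that E 2 carries its own limit. Its reason for ending participation is that sampling is integral, and the protocol says several times that the genetic sample is not. On that reasoning the sentence reaches only the mandatory bloods. D 2 is also the specific rule: it has its own heading on withdrawal from genetic research, and it makes the principal investigator responsible for seeing that subjects understand they can leave freely. None of the genetics passages sends a site to E 2. For the harm to occur, a site would have to go to E 2 unprompted and let it override D 2.

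Much of this stands. It is why the conflict is one of literal reading and why the consequence is likely to be rare. It does not remove the point, because the limit has to be inferred and a site looking for disposal steps will find them only in E 2.

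Three stronger readings are tempting, and the documents do not support them:

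- *Power is at risk.* A reader might subtract lost events from the target. No number of affected patients can be derived, and the trial runs until its event target is reached, so a few lost patients would mainly be absorbed by slightly longer follow-up.
- *Patients are given a promise that E 2 breaks.* D 2 is protocol text addressed to sites. The consent form is not in the text supplied, so what patients are told cannot be judged.
- *E 2 also contradicts Section 7.3.* That section reserves withdrawal for patients who refuse all further assessment or contact, but it concerns consent to the study, not to the use of samples. The two sit uneasily together without contradicting each other directly.

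**Conclusion.** The point holds as a minor internal inconsistency. E 2 is an operative instruction, it makes no exception, and for the optional genetic sample its literal result is the opposite of D 2's.

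The conclusion rests on reading E 2 as written. If sites all took it to mean the mandatory samples only, nothing would go wrong in practice, but the protocol does not say so. The number of patients affected cannot be derived. That it is probably very small is a judgement, based on the fact that a patient would have to give the optional consent, withdraw it, and be at a site that applied E 2 literally. No stated design figure is affected. What remains is the risk of ending endpoint follow-up needlessly in an individual randomised patient.

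**What to change.** Reconcile E 2 with D 2 by adding one sentence to E 2, for example: *Withdrawal of consent for the optional genetic sample leads only to disposal of that sample and documentation of the disposal; it does not end study participation or follow-up.*

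The cost is small. The sentence can be carried in the next amendment, with whatever ethics-committee approval Appendix A 1 requires, and a short note to the approximately 400-500 sites. No analysis, analysis set, event target or sample size changes. Whether the consent form needs a matching edit should be checked against the form itself.
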